14.5 Prospective Validation of Survival Scale

We have previously designed and validated a scale which can predict 90 day mortality among patients with hematological malignancies enrolled in Phase I and II clinical trials [*Jamal 2012*]. This scale uses 5 easy to measure, objective clinical variables, including albumin, LDH, diagnosis (AML vs non AML), platelet count and alkaline phosphatase. Each is attributed one point. A patient having 3 or more points has up to a 40% chance of mortality within 3 months of treatment on a clinical trial. The initial validation did not include patients with CLL. We therefore intend to validate this scale in CLL in the context of this trial.

The scale will be applied to each individual patient and mortality risk calculated. A Kaplan Meier survival curve will be generated and hazard ratio for death estimated comparing low and high risk patients within this study, in order to determine the ability of the scale to distinguish mortality risk between these two groups.

AMEND #3: 2016-AUG-24

15.0 PUBLICATION POLICY

15.1 Authorship of Papers, Meeting Abstracts, Etc

15.1.1 The results of this study will be published. Prior to trial activation, the chair will decide whether to publish the trial under a group title, or with naming of individual authors. If the latter approach is taken, the following rules will apply:

- The first author will generally be the chair of the study.
- A limited number of the members of the Canadian Cancer Trials Group and Novartis, may be credited as authors depending upon their level of involvement in the study.
- Additional authors, up to a maximum of 15, will be those who have made the most significant contribution to the overall success of the study. This contribution will be assessed, in part but not entirely, in terms of patients enrolled and will be reviewed at the end of the trial by the study chair.

15.1.2 In an appropriate footnote, or at the end of the article, the following statement will be made:

"A study coordinated by the Canadian Cancer Trials Group. Participating investigators included: (a list of the individuals who have contributed patients and their institutions)."

15.2 Responsibility for Publication

It will be the responsibility of the Study Chair to write up the results of the study within a reasonable time of its completion. If after a period of six months following study closure the manuscript has not been submitted, the central office reserves the right to make other arrangements to ensure timely publication.

Dissemination of Trial Results

CCTG will inform participating investigators of the primary publication of this trial. The complete journal reference and, if where publicly available, the direct link to the article will be posted on the Clinical Trial Results public site of the CCTG web site (<http://www.ctg.queensu.ca>).

15.3 Submission of Material for Presentation or Publication

Material may not be submitted for presentation or publication without prior review by Novartis, the CCTG Senior Investigator, Senior Biostatistician, Study Coordinator, and approval of the Study Chair. Individual participating centres may not present outcome results from their own centres separately. Supporting groups and agencies will be acknowledged.

AMEND #3: 2016-AUG-24

16.0 ETHICAL, REGULATORY AND ADMINISTRATIVE ISSUES

16.1 Regulatory Considerations

All institutions in Canada must conduct this trial in accordance with International Conference on Harmonization-Good Clinical Practice (ICH-GCP) Guidelines.

This trial is being conducted under a Clinical Trial Application (CTA) with Health Canada. As a result, the conduct of this trial must comply with Division 5 of the Canadian Regulations Respecting Food and Drugs (Food and Drugs Act).

16.2 Inclusivity in Research

CCTG does not exclude individuals from participation in clinical trials on the basis of attributes such as culture, religion, race, national or ethnic origin, colour, mental or physical disability (except incapacity), sexual orientation, sex/gender, occupation, ethnicity, income, or criminal record, unless there is a valid reason (i.e. safety) for the exclusion.

In accordance with the Declaration of Helsinki and the Tri-Council Policy Statement (TCPS), it is the policy of CCTG that vulnerable persons or groups will not be automatically excluded from a clinical trial (except for incompetent persons) if participation in the trial may benefit the patient or a group to which the person belongs.

However, extra protections may be necessary for vulnerable persons or groups. It is the responsibility of the local investigator and research ethics board (REB) to ensure that appropriate mechanisms are in place to protect vulnerable persons/groups. In accordance with TCPS, researchers and REBs should provide special protections for those who are vulnerable to abuse, exploitation or discrimination. As vulnerable populations may be susceptible to coercion or undue influence, it is especially important that informed consent be obtained appropriately.

Centres are expected to ensure compliance with local REB or institutional policy regarding participation of vulnerable persons/groups. For example, if a vulnerable person/group would be eligible for participation in a CCTG clinical trial under this policy but excluded by local policy, it is expected that they would not be enrolled in the trial. It is the centre's responsibility to ensure compliance with all local SOPs.

It is CCTG's policy that persons who cannot give informed consent (i.e. mentally incompetent persons, or those physically incapacitated such as comatose persons) are not to be recruited into CCTG studies. It is the responsibility of the local investigator to determine the subject's competency, in accordance with applicable local policies and in conjunction with the local REB (if applicable).

Subjects who were competent at the time of enrolment in the clinical trial but become incompetent during their participation do not automatically have to be removed from the study. When re-consent of the patient is required, investigators must follow applicable local policies when determining if it is acceptable for a substitute decision maker to be used. CCTG will accept re-consent from a substitute decision maker. If this patient subsequently regains capacity, the patient should be re-consented as a condition of continuing participation.

16.3 Obtaining Informed Consent

It is expected that consent will be appropriately obtained for each participant/potential participant in an CCTG trial, in accordance with ICH-GCP section 4.8. The centre is responsible for ensuring that all local policies are followed.

Additionally, in accordance with GCP 4.8.2, CCTG may require that participants/potential participants be informed of any new information may impact a participant's/potential participant's willingness to participate in the study.

Based upon applicable guidelines and regulations (Declaration of Helsinki, ICH-GCP), a participating investigator (as defined on the participants list) is ultimately responsible, in terms of liability and compliance, for ensuring informed consent has been appropriately obtained. CCTG recognizes that in many centres other personnel (as designated on the participants list) also play an important role in this process. In accordance with GCP 4.8.5, it is acceptable for the Qualified Investigator to delegate the responsibility for conducting the consent discussion.

CCTG requires that each participant sign a consent form prior to their enrollment in the study to document his/her willingness to take part. CCTG may also require, as indicated above, that participants/potential participants be informed of new information if it becomes available during the course of the study. In conjunction with GCP 4.8.2, the communication of this information should be documented.

CCTG allows the use of translators in obtaining informed consent. Provision of translators is the responsibility of the local centre. Centres should follow applicable local policies when procuring or using a translator for the purpose of obtaining informed consent to participate in a clinical trial.

In accordance with ICH-GCP 4.8.9, if a subject is unable to read then informed consent may be obtained by having the consent form read and explained to the subject.

16.3.1 Obtaining Consent for Pregnancy/Exposure Reporting

Information from and/or about the subject (i.e. the pregnant female, the newborn infant, male partner, exposed individual) should not be collected about or from them unless or until they are a willing participant in the research. The rights and protections offered to participants in research apply and consent must be obtained prior to collecting any information about or from them.

Trial-specific consent forms for "Pregnancy Follow-up" and "Exposure Follow-up" can be found on the trial webpage. The appropriate consent form must be used to obtain consent from any non-trial participant (such as the pregnant partner or exposed individual).

Participants will not be withdrawn from the main trial as a result of refusing or withdrawing permission to provide information related to the pregnancy/exposure. Similarly, male participants will not be withdrawn from the main study should their partner refuse/withdraw permission.

Obtaining Consent for Research on Children

In the case of collecting information about a child (i.e. the child resulting from a pregnant participant/partner or an exposed child), consent must be obtained from the parent/legal guardian.

AMEND #3: 2016-AUG-24

For reporting an exposure, the parent/guardian is required to sign an “exposure follow-up” consent form (even if they are a participant in the main study) prior to collecting information about the child.

16.4 Discontinuation of the Trial

If this trial is discontinued for any reason by the CCTG all centres will be notified in writing of the discontinuance and the reason(s) why. If the reason(s) for discontinuance involve any potential risks to the health of patients participating on the trial or other persons, the CCTG will provide this information to centres as well.

If this trial is discontinued at any time by the centre (prior to closure of the trial by the CCTG), it is the responsibility of the qualified investigator to notify the CCTG of the discontinuation and the reason(s) why.

Whether the trial is discontinued by the CCTG or locally by the centre, it is the responsibility of the qualified investigator to notify the local Research Ethics Board and all clinical trials subjects of the discontinuance and any potential risks to the subjects or other persons.

16.5 Retention of Patient Records and Study Files

All essential documents must be maintained as per C.05.012 and in accordance with ICH-GCP.

The Qualified Investigator must ensure compliance with the Regulations and the GCP Guideline from every person involved in the conduct of the clinical trial at the site.

Essential documents must be retained for 25 years following the completion of the trial at the centre (25 years post final analysis, last data collected, or closure notification to REB, whichever is later), or until notified by CCTG that documents no longer need to be retained.

In accordance with GCP 4.9.7, upon request by the monitor, auditor, REB or regulatory authority, the investigator/institution must make all required trial-related records available for direct access.

CCTG will inform the investigator/institution as to when the essential documents no longer need to be retained.

16.6 Centre Performance Monitoring

This study is eligible for inclusion in the Centre Performance Index (CPI).

Forms are to be submitted according to the schedule in the protocol. There are minimum standards for performance.

16.7 On-Site Monitoring/Auditing

CCTG site monitoring/auditing will be conducted at participating centres in the course of the study as part of the overall quality assurance program. The monitors/auditors will require access to patient medical records to verify the data, as well as essential documents, standard operating procedures (including electronic information), ethics and pharmacy documentation (if applicable).

AMEND #3: 2016-AUG-24

As this trial is conducted under a CTA with Health Canada, your site may be subject to an inspection by the Health Canada Inspectorate.

Novartis has reserved the right to audit participating centres. Audits may only be conducted after consultation with CCTG.

16.8 Case Report Forms

A list of forms to be submitted, as well as expectation dates, are to be found in Appendix IV.

This trial will use a web-based Electronic Data Capture (EDC) system for all data collection. For details of accessing the EDC system and completing the on-line Case Report Forms please refer to the "Registration and Data Management Guidebook" posted on the IND. 216 area of the CCTG web-site (www.ctg.queensu.ca).

17.0 CORRELATIVE BLOOD WORK

Collection of Lymphocytes From the Peripheral Blood (Mandatory)

The collection of malignant lymphocytes is an important part of this trial. This is mandatory for participation in the study.

See Lab Manual posted on the IND 216 webpage for complete details.

17.1 Objectives

Samples will be used to determine:

- 1) In vitro sensitivity to buparlisib using the MTT (3-(4,5-dimethylthiazol-2-yl)-2,5-diphenyltetrazolium bromide) assay, correlated with clinical response.
- 2) Level of biomarkers predictive of sensitivity to buparlisib by protein isolation and flow cytometry. The candidate proteins include raptor and p70S6K which are involved in the PI3K signaling pathway.
- 3) In relapsing patients after treatment with buparlisib, protein, RNA and DNA will be isolated in order to identify mechanisms of resistance to buparlisib and potentially to other PI3K inhibitors.

17.1.1 Rationale for Correlative Blood Work

PI3K inhibitors are effective therapies for CLL. However not all patients respond and many relapse as evidenced by the recent publication of data on idelalisib [Furman 2014]. The correlative blood work proposed here aims to identify by MTT assay and by the identification and validation of biomarkers, those patients likely to respond to therapy. Recent translational studies demonstrated that simultaneous low raptor and p70S6K protein expression may be predictive of sensitivity to buparlisib *in-vitro* [Amrein 2013]. This clinical trial aims to confirm if these two proteins involved in the PI3K signaling pathway, can be used as biomarkers to predict clinical response of patients with CLL to buparlisib therapy. This will allow for better selection of patients for PI3K inhibitor therapy in the future. In addition, mechanisms of resistance to PI3K inhibitors is unknown; the research to be conducted using patient samples will allow exploration of resistance mechanisms.

17.2 PIK3CA Gene Amplification Analysis

PI3K mutations are well described in solid tumours (particularly in PIK3CA-the gene which encodes p110 α), however activating PI3K mutations are noticeably absent in B cell malignancies such as CLL [*Marincevic 2009; Ortiz-Maldonado 2015; Thorpe 2015*]. A recent study of 188 patients with CLL showed no point mutations in p110 α , - δ or - β isoforms, despite PI3K pathway constitutive activation [*Brown 2012*]; however, the same study demonstrated that amplifications of the PIK3CA locus were present in 6% of CLL patients (with 80% of the CLL cohort investigated being treatment naïve). Thus, gene amplification will be studied as a mechanism for PI3K pathway activation in this relapsed/refractory CLL population, by investigation of the copy number status of the genes PIK3CD and PIK3CA, which encode the p110 δ and p110 α isoforms respectively. Gene amplification will be measured using digital PCR, a highly sensitive and accurate methodology, in all patients treated on the IND 216 trial, both prior to therapy and after disease progression correlating with development of drug resistance.

Univariate analysis will be attempted to investigate for any association of copy number variation with known clinical characteristics and prognostic factors (age, gender, number of prior lines of therapy, cytogenetics, unmutated IgHV status and response and duration of response to buparlisib).

AMEND #1: 2015-OCT-22

APPENDIX I - PATIENT EVALUATION FLOW SHEET

Required Investigations	Prestudy (within 7 days prior to registration unless otherwise indicated)	Days 1 & 14 cycle 1 and 2; thereafter day 1 each cycle (and as clinically indicated)	Day 1 each cycle	At 8, 16 and 24 weeks from registration, and thereafter every 12 weeks	4 weeks after Off Protocol Therapy
History and Physical					
Physical Exam (including height, weight)	X		X		X
ECOG Performance Status					
Pulse, blood pressure					
Clinical tumour / organomegaly measurements (if applicable)			X	To confirm PR or CR and as clinically indicated ¹	
Hematology					
CBC, differential (including lymphocytes)	X	X			X (and at 8 weeks if required to confirm PR or CR)
PT, PTT	X		As clinically indicated		
Biochemistry¹					
creatinine, potassium, bilirubin, AST, ALT, alkaline phosphatase, LDH, albumin, calcium, glucose (fasting), phosphate ² , uric acid ²	X	X			X
lipase		X			
HbA1c (if diabetic), Beta 2 microglobulin	X				
Radiology					
Neck/chest/abdominal/pelvic CT	X ³			X ⁴	X ⁴
Assessment for MRD (optional)				X (at CR only)	X (at CR only)
Cardiac Investigations					
12-lead ECG	X		As clinically indicated		
MUGA/LVEF	X ⁵		As clinically indicated		
Other Investigations					
Pregnancy test (serum or urine for women of childbearing potential only)	X				
Fluorescence in situ hybridization	X ⁵				
Direct antiglobulin test (DAGT)	X				
Bone Marrow Aspirate and Biopsy	X ⁶			X ⁷	X ⁷
Immunoglobulin variable region (IgVH) mutation status	X ⁸				
Mood Questionnaires ⁹	X	X			X ¹⁰
Hepatitis B surface antigen (HBsAg)	X ¹¹				
Hepatitis C serology	X ¹¹				
Correlative Blood Work					
Peripheral Blood (See Section 17 and Laboratory Manual for details)	X ¹¹			X (at progression if applicable)	
Adverse Events					
CTCAE v 4.0	X		continuously		

footnotes on next page ...

AMEND #1: 2015-OCT-22; AMEND #3: 2016-AUG-24

1. See section 8 for additional monitoring of AST/ALT and bilirubin with hepatic toxicity.
2. The first 4 patients treated on study will require monitoring for tumour lysis on days 1, 2 and 3 of cycle 1 only: calcium, creatinine, potassium, phosphate and uric acid. CCTG will notify centres if this applies at the time of registration.
3. Within 21 days prior to registration (within 28 days if negative).
4. Patients with an unconfirmed PR or CR should have scans repeated after 8 weeks to confirm response. Scans should also be repeated at 8, 16 and 24 weeks from study registration and thereafter every 12 weeks.
5. Within 28 days prior to registration (only if symptoms suggestive or history of cardiovascular disease).
6. Within 28 days prior to registration for routine local pathology to assess CLL
7. At time CR criteria first met, 8 weeks later to confirm sustained CR, or if cytopenia of uncertain cause.
8. Can be done any time prior to registration on peripheral blood or bone marrow.
9. Patient self-rating mood questionnaires (PHQ-9 and GAD-7) are posted on the I216 website.
10. Mood questionnaires also required to be completed by patient at the End of Treatment visit.
11. Within 28 days prior to registration.

APPENDIX II - PERFORMANCE STATUS SCORES

ECOG (Zubrod)	
Score	Description
0	Fully active, able to carry on all pre-disease performance without restriction.
1	Restricted in physically strenuous activity but ambulatory and able to carry out work of a light or sedentary nature, e.g. light housework, office work.
2	Ambulatory and capable of all self care but unable to carry out any work activities. Up and about more than 50% of waking hours.
3	Capable of only limited self care; confined to bed or chair more than 50% of waking hours.
4	Completely disabled. Cannot carry on any self care. Totally confined to bed or chair.

AMEND #3: 2016-AUG-24

APPENDIX III - DRUG DISTRIBUTION, SUPPLY AND CONTROL

Drug Distribution

Buparlisib will be sent by Novartis to participating centres.

Drug Labelling

Drug supplies for this study will be labelled in accordance with Health Canada regulations. The labels contain all information required under the drug labelling regulations.

Initial Drug Supply

Once a centre is locally activated (following receipt and review of all required documentation), the CCTG will authorize a start-up supply of buparlisib to be shipped directly to the centre. The drug will be shipped to the centre within 5 working days of local activation. Drug accountability and drug re-order forms will be included with the drug shipment and are also available on the trial website: (www.ctg.queensu.ca/trials/ind/216/216.html).

Drug Ordering (Re-supply)

Fax a copy of the buparlisib drug re-order form (available at www.ctg.queensu.ca/trials/ind/216/216.html) to Novartis.

Please allow sufficient time for shipment of drug.

Drug Accountability

The investigational products are to be prescribed only by the investigator and co-investigators on the participants list. Under no circumstances will the investigator allow the drug to be used other than as directed by the protocol. Accurate records must be maintained accounting for the receipt of the investigational product and for the disposition of the product (Drug Accountability Log).

Drug Destruction or Return:

Details to be supplied at the time of study closure.

**PLEASE NOTE **

DRUG FROM THIS SUPPLY IS TO BE USED ONLY

FOR PATIENTS REGISTERED ON THIS STUDY

Study drug shipped to participating centres may be transferred from the main hospital pharmacy to a satellite pharmacy, provided separate drug accountability records are maintained in each pharmacy. Investigational agent may NOT however, be transferred to pharmacies or physicians outside the participating centre.

APPENDIX IV - DOCUMENTATION FOR STUDY

Follow-up is required for patients from the time of registration and will apply to all eligible and ineligible patients. This trial will use a web-based Electronic Data Capture (EDC) system for all data collection including SAE reporting (see section 11.0 for details regarding SAE reporting). For details about accessing the EDC system and completing the on-line Case Report Forms, please refer to the Data Management Guidebook posted on the IND 216 area of the CCTG website (www.ctg.queensu.ca).

Form	To be Completed/Submitted Electronically:	Supporting Documentation to be sent using Supporting Document Upload Tool
PATIENT ENROLLMENT FOLDER	Must be completed at time of registration to confirm eligibility.	
BASELINE REPORT	Due within 2 weeks of patient registration.	Copies of the signed signature page(s) of the consent form; relevant pathology and radiology reports; mood questionnaires; ECG reports; MUGA/LVEF report (if applicable)
TREATMENT REPORT	To be completed every 28 days (i.e. after each cycle). Due within 2 weeks of end of cycle. This form documents treatment, adverse events, investigations and response assessment for each cycle.	Relevant radiology reports. Patient diary. Mood questionnaires.
CORRELATIVE BLOOD WORK	See Section 17 and Laboratory Manual for details.	
END OF TREATMENT REPORT	To be completed when patient permanently discontinues protocol treatment. Due within 2 weeks of end of protocol treatment.	Mood questionnaires.
4 WEEK POST TREATMENT REPORT	To be completed once on all patients, 4 weeks after the end of the last cycle. Due within 2 weeks after contact with patient.	Relevant radiology reports.
FOLLOW-UP REPORT	Continued follow-up is not required for patients who go off protocol treatment with progressive disease , except to document ongoing toxicities (until resolved to \leq grade 2) and late toxicities (including second malignancies). For patients who go off protocol therapy with suspected PR or CR, an 8 week confirmatory response assessment including CT scanning will be required as per sections 9.1 and 10.4, if not already performed. For patients who go off protocol treatment with objective CR, PR or SD ongoing , a follow-up report will be required every 3 months until relapse/progression. Due within 2 weeks after contact with patient.	Relevant radiology reports.
RELAPSE/PROGRESSION REPORT	To be completed at the time of disease relapse or progression. Due within 2 weeks after contact with patient.	Relevant radiology reports.

continued on next page ...

Form	To be Completed/Submitted Electronically:	Supporting Documentation to be sent using Supporting Document Upload Tool
DEATH REPORT	Required only on patients who die during protocol therapy, within 30 days after last dose, or within the protocol defined follow-up period for patients with response or stable disease ongoing.* Due within 2 weeks of knowledge of death.	Autopsy report, if done.
SERIOUS ADVERSE EVENT REPORT FORM	All reportable serious adverse events must be reported as described in Section 11.0. All reportable serious adverse events must be reported as described in Section 11.0. Preliminary CCTG Serious Adverse Event Report due within 24 hours. Updated CCTG Serious Adverse Event Report due within 7 days .	
* NB It is the investigator's responsibility to investigate and report the date/cause of death of any patient who dies during this period. Any death that occurs during this period and that is thought to be treatment related must also be reported as a Serious Adverse Event as described in Section 11.		

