9.3 Evaluation After Protocol Treatment

All patients will be seen 4 weeks after the end of the last cycle (4 Week Post Treatment Report).

Patients whose treatment is permanently discontinued due to an adverse event or non-hepatic clinically significant laboratory value, should be followed as clinically indicated until resolved to \leq grade 2. See Section 8.4.3 for more detailed guidance on patients who discontinue study treatment due to hepatic toxicity.

Follow-up beyond the 4 week treatment report is not required for patients who go off protocol treatment with progressive disease, except to document ongoing toxicities (until resolved to \leq grade 2), late toxicities (including second malignancies) and death if within 30 days of last dose.

For patients who go off protocol treatment with objective CR, PR or SD ongoing, follow up including response assessment will be required every three months until relapse/progression (Follow-Up Report). If the patient starts new anticancer therapy, contact the study coordinator to discuss whether further follow-up is required.

For patients who go off protocol therapy with suspected PR or CR, an 8 week confirmatory response assessment including CT scanning will be required as per Sections 9.1 and 10.4, if not already performed.

A Death Report is only required if death occurs within 30 days of last dose or if patient dies before progression/relapse; due within 2 weeks of knowledge of death (see Appendix IV –Documentation for Study).

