10.0 CRITERIA FOR MEASUREMENT OF STUDY ENDPOINTS

10.1 Definitions

10.1.1 Evaluable for Response

All patients who have received at least one cycle of therapy and have their disease re-evaluated will be considered evaluable for response (exceptions will be those who exhibit objective disease progression prior to the end of cycle 1 who will also be considered evaluable). Patients on therapy for at least this period and who meet the other listed criteria will have their response classified according to the definitions set out below, as recommended by Revised International Workshop on Chronic Lymphocytic Leukemia 2008 [*Hallek 2008*] and incorporating updated recommendations for refinement of clinical trial endpoints when using novel targeted agents [*Cheson 2012*].

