 - The progression of any cytopenia (unrelated to autoimmune cytopenia), as documented by a decrease of Hb levels by more than 20 g/L (2 g/dL) or to less than 100 g/L, or by a decrease of platelet counts by more than 50% or to less than $100 \times 10^9/L$, which occurs at least 3 months after treatment, defines disease progression, if the marrow biopsy demonstrates an infiltrate of clonal CLL cells.

Note:

B cell receptor targeted drugs can mobilize CLL cells from tissues into the peripheral blood, interfering with their homing. This characteristic pharmacologic action can be prominent early in therapy, but can also persist over time. This occurrence should not be confused with PD unless the treated patient develops other CLL-related signs or symptoms of PD. In the absence of other objective evidence of PD, **lymphocytosis alone should not be considered an indicator of PD** [Cheson 2012].

Stable Disease (SD): Patients who have not achieved a CR or a PR, and who have not exhibited progressive disease, will be considered to have stable disease (which is equivalent to a nonresponse).

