10.7 Progression-Free Survival

Progression-free survival (PFS) is defined as the time from study entry until disease progression or death.

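### Section 9.3 and Appendix IV set different triggers for the Death Report, so a PFS death in a patient who stops without progression and without re-evaluation may go unrecorded

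*Protocol*

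**What the plan says.** **Endpoint.** Section 10.7: "Progression-free survival (PFS) is defined as the time from study entry until disease progression or death". Response status plays no part in whether a death counts.

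**Death Report, Section 9.3.** "A Death Report is only required if death occurs within 30 days of last dose or if patient dies before progression/relapse". The second limb also does not depend on response status. The same sentence sends the reader to Appendix IV.

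**Death Report, Appendix IV.** "Required only on patients who die during protocol therapy, within 30 days after last dose". The row then adds a third group, which is the only one to cover later deaths: those "within the protocol defined follow-up period for patients with response or stable disease ongoing". The row's footnote makes the investigator responsible for the date and cause of death, but only for deaths in that period, so it carries the same limit.

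**Follow-up.** Section 9.3: "For patients who go off protocol treatment with objective CR, PR or SD ongoing, follow up including response assessment will be required". The interval is three months, and the requirement ends at relapse or progression. The Follow-up Report row of Appendix IV uses the same three categories. The last contact scheduled for everyone is earlier: "All patients will be seen 4 weeks after the end of the last cycle".

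**Who has a response category.** Section 10.1.1: "All patients who have received at least one cycle of therapy and have their disease re-evaluated will be considered evaluable for response", with early objective progression as the exception. Section 10.4 defines stable disease as what is left over: "Patients who have not achieved a CR or a PR, and who have not exhibited progressive disease, will be considered to have stable disease".

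**Analysis.** The SAP lists a Kaplan-Meier plot for PFS and gives no censoring rule.

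**The concern.** The two Death Report triggers disagree for one kind of patient: someone who stops treatment (for toxicity or by request, say) without progression, has no disease re-evaluation, and dies more than 30 days after the last dose. Section 9.3 wants a form; Appendix IV, read literally, does not. Sites are likely to follow Appendix IV, because Section 9.0 tells them to submit documentation by its schedule and Section 16.8 points to it for the list of forms and due dates.

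The follow-up rule has the same gap. After the four-week visit no scheduled contact is laid down for this patient, so a later progression or death might not come to light at all. In the Kaplan-Meier plot the patient would then probably appear as an early censored observation. If patients who leave this way fare worse than the rest, the curve reads too high. The 90-day mortality scale in Section 14.5 draws on the same death data: a patient whose last dose is on day 28 and who dies on day 80 dies 52 days after that dose, outside the 30-day window but inside 90 days.

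**Working it through.** No figure in the plan bears on this point, so there is none to reproduce. The check is a comparison of the texts, followed by arithmetic on assumed counts.

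**Step 1. Which deaths need a form**

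| Death | Section 9.3 | Appendix IV | PFS (10.7) |
|---|---|---|---|
| On treatment or within 30 days of last dose | Form | Form | Event, unless already progressed |
| Later, CR, PR or SD ongoing, in follow-up | Form | Form | Event |
| Later, after documented progression | No form | No form | Event already counted at progression |
| Later, no progression, never re-evaluated | Form | No form, unless the site classes the patient as SD | Event |

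Only the last row is in conflict.

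**Step 2. Effect of missed deaths on the curve**

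Assume 12 patients (the evaluable number for the PI3K-inhibitor-naïve cohort in Section 14.2) and 4 true PFS events by the time of interest. Assume also that a patient whose death is missed is censored before any other event, and that there is no other censoring. Kaplan-Meier then reduces to event-free patients divided by patients still contributing.

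- Truth: 8/12 = 66.7%, with standard error √(0.667 × 0.333 / 12) = 13.6 points.
- One death missed: 8/11 = 72.7%, a shift of 6.1 points.
- Two deaths missed: 8/10 = 80.0%, a shift of 13.3 points, about one standard error.
- All 29 patients with 9 true events: 20/29 = 69.0%. One death missed gives 20/28 = 71.4%, a shift of 2.5 points.

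**Step 3. When this is a bias**

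Step 2 conditions on the lost patient having died. If the follow-up gap removes unassessed patients whether or not they have an event, and their risk equals the others', the estimate does not drift. For example, if 3 of the 12 leave and 1 of those 3 would have had an event, the remaining 9 have 3 events, and 6/9 = 66.7%, as in truth.

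With unequal risk, assume exponential PFS with a 9-month median, a fraction g unassessed and censored at month 2, and twice the hazard for them from month 2. The observed curve at 6 months is 2^(−6/9) = 63.0%. The true value is (1 − g) × 2^(−6/9) + g × 2^(−(2 + 2×4)/9), where the last power is 46.3%.

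- g = 10%: 0.9 × 63.0 + 0.1 × 46.3 = 61.3%, a bias of 1.7 points.
- g = 20%: 0.8 × 63.0 + 0.2 × 46.3 = 59.7% (59.6% by simulation), a bias of about 3.4 points.

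This scenario loses progressions as well as deaths, so it describes the follow-up gap as a whole. The median, g and the hazard ratio are assumptions; the documents give none of them.

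**The case against.** The strongest reply is that the two texts agree once stable disease is read as Section 10.4 defines it. It is the residual category, and Section 10.4 also opens by saying that every patient has a best response classified. A patient off treatment without progression would then be stable disease, and both the three-monthly follow-up and the Appendix IV Death Report would apply. This reading is possible but not secure: Section 10.1.1 limits classification to patients with one cycle and a re-evaluation, and Section 9.3 speaks of objective stable disease. Sites could reasonably differ.

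Other parts of the reply narrow the point:

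- A reader might infer that everyone who stops before the week-8 CT is affected. The documents do not support that. Section 9.1 schedules blood counts with lymphocytes on days 1 and 14 of the first two cycles and clinical measurements on day 1 of each cycle, lymphocyte count is a response criterion in Section 10.4, and the Treatment Report includes a response assessment each cycle. Re-evaluation does not require a CT.
- Section 12.1 asks for efforts to continue follow-up after early stopping, and Appendix IV opens by applying follow-up to all registered patients. These statements reduce the loss, but set no schedule or death form for the patient in question.
- A reader might put each missed death at 1/12, about 8 points, and two at about 17 points, more than one standard error. That holds only if the patient is counted as event-free at the time of interest. If the patient is censored early, the shifts are those in Step 2.
- A reader might infer that harm is hidden. Section 11.1 still requires expedited reporting of unexpected, treatment-related serious events after 30 days, and late toxicities are collected. What may be lost is the PFS event.

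**Conclusion.** The contradiction is real and the point is minor. Section 9.3 and Appendix IV give different answers for a death more than 30 days after the last dose in a patient with neither progression nor re-evaluation, and neither schedules follow-up for that patient after the four-week visit. Followed as written, Appendix IV can leave out a death that Section 10.7 counts. It does not certainly do so, because the residual definition of stable disease may lead a site to file the form.

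The size depends on how many such patients there are, which the documents do not say; the group is probably small. One missed death in 12 patients is worth about 6 points on the curve and two about 13, under the stated assumption of 4 true events and early censoring. An upward bias on average requires these patients to progress or die more often than the rest. That they would be censored is itself inferred, since neither document gives a PFS censoring rule.

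A reader should not carry this over to the trial's main conclusion. The effect is confined to secondary, descriptive survival outputs; no decision rule uses PFS, and the response endpoint and its two-stage rule in Section 14.2 are unaffected.

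**What to change.** 1. Reword the Death Report row of Appendix IV to match Section 9.3: a report for any death on therapy, within 30 days of the last dose, or before documented progression, whatever the response status.
2. In Section 9.3 and in the Follow-up Report row of Appendix IV, extend the three-monthly report of progression and vital status to all patients off treatment without documented progression, naming those not assessed. Changing the Death Report row alone would not be enough, because without a scheduled contact the site may not learn of the death.
3. In the SAP, add a line stating how PFS is censored for patients with no assessment after baseline.

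The cost is a wording change in Section 9.3 and two Appendix IV rows, one SAP sentence, and a few extra follow-up and death forms. Treatment rules, sample size and the primary analysis do not change.
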